6.0 STUDY PROCEDURES

6.1 Screening/Baseline Procedures

Assessments performed exclusively to determine eligibility for this study will be done only after obtaining informed consent. Assessments performed for clinical indications (not exclusively to determine study eligibility) may be used for baseline values even if the studies were done before informed consent was obtained. Frequent monitoring of clinical chemistry and hematology is routine in HCT patients. This study does not require specific laboratory monitoring other than specified below.

6.1.1 Informed Consent

6.1.2 **Demographics**

6.1.3 Review subject eligibility criteria

6.1.4 **Review concomitant medications** (immunosuppressants and GVHD prophylaxis medications only)

6.1.5 Adverse event assessment

Baseline adverse events will be assessed and preexisting conditions will be recorded. See Section 8.0 for Adverse Event monitoring and reporting.

6.1.6 Serum chemistries (within 3 days prior to enrollment)

ALT/SGPT, AST/SGOT, and total bilirubin are required for assessment of exclusion criteria within 3 days prior to enrollment.

6.2 Follow-Up Procedures

The following outlines the minimum frequency of follow-up evaluations, it is anticipated that the majority of patients will be evaluated more frequently.

During the first 4 weeks of participation (i.e., through the primary endpoint), patients will be seen at least weekly for assessment of their GVHD. During the second four weeks patients should be seen at least every other week, although it is anticipated that most patients will be seen more frequently, i.e., weekly. Patients will also be evaluated at study day 86 (30 days from completion of treatment). In addition, relapse, survival, and chronic GVHD will be reported at six and twelve months from treatment initiation.

Infections, as defined in sections 7.2.3 to 7.2.5 will be closely monitored on this study. In our preliminary data (section 1.2), 100% of CMV infections requiring treatment developed within 90 days from starting systemic GVHD treatment, 100% of EBV infections requiring treatment, 85% of bacteremia, and 75% of invasive fungal infections. All patients who developed at least one serious infection did so within 90 days. Given these data, we will monitor for serious infections from start of itacitinib treatment through study day 90.

Follow-up studies are detailed in the Time and Events Table below.

	CALENDAR BASED ASSESSMENTS											
	Screening	Study day 0	Study day 7	Study day 14	Study day 21	Study day 28 ¹	Study day 42	Study day 56	Study day 90	Study day 180	Study day 365	GVHD Flare ⁷
Windows	Newly diagnosed acute GVHD in need of systemic treatment +/- 1 day	Within 4 days of Ann Arbor Score Notification	+/- 2 days	+/- 2 days	+/- 2 days	+/- 1 day	+/- 3 days	+/- 3 days	+/- 5 days	+/- 14 days	+/- 14 days	+/- 3 days
Eligibility Review	х											
Concomitant Medication Review ²	х	х	х	х	х	х	х	х	х			
Adverse Event Evaluations ³	х	Adve	erse event	s will be rep	orted from s Report seri	study day 0 ous adverse	through 30 e events as	days after t they occur.	he last dos	e of study dru	g.	
Infections		Infec	tions as d	efined in se	ctions 7.2.3	-7.2.5 will be	e reported f	rom study c	lay 0 throug	gh study day 9	00	
Serum Chemistry	Х											
GVHD Staging ⁴	Х	Х	х	х	х	х	х	х	х			х
Itacitinib			200 mg daily induction cycle 200 mg daily maintenance cycle (responders only) ⁵									
Survival, Relapse & Chronic GVHD Status										х	х	
	CORRELATIVE STUDIES											
5 ml serum ⁶	Х	Х	Х	х	х	х						х

¹ The primary endpoint is assessed on day 28 ±1 day

- ² Concomitant medication review will record **only** immunosuppressants and other drugs administered during the reporting period for GVHD prevention and treatment.
- ³ Serious adverse events are reported as they occur. Other adverse events can be batch reported after the patient has been followed for 30 days from the last dose of study drug.
- ⁴ GVHD staging will follow the detailed guidelines provided in the MAGIC Acute GVHD Staging Guidance. During the maintenance cycle GVHD staging is required every other week. GVHD staging and treatment should be reported weekly through day 100 post-HCT for patients co-enrolled on the MAGIC observational study as per the observational study calendar of events.

⁵ Itacitinib maintenance dosing is only given to patients who respond to the induction cycle

⁶ Serum samples will be banked for correlative studies. To avoid unnecessary sample collection, when GVHD driven samples are collected within 3 days of a scheduled calendar based sample, the calendar based sample should not be collected.

⁷ Collect GVHD staging data and a serum sample if GVHD flares during the study.

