7.2.3 Infectious Toxicities

Infections, including serious and/or life-threatening infections, are common in patients who undergo HCT. MAGIC clinical trial practice requires the reporting of any life-threatening infection as defined by the Blood and Marrow Transplant Clinical Trials Network grade 3 (see Appendix B for further details).

Grade 3 Bacterial Infections:

- a. Bacteremia with deep organ involvement
- b. Severe sepsis with bacteremia
- c. Fasciitis requiring debridement
- d. Pneumonia requiring intubation
- e. Brain abscess or meningitis without bacteremia
- f. Clostridium difficile toxin positive stool with toxic dilatation or renal insufficiency with/without diarrhea.

Grade 3 Fungal Infections:

- a. Fungemia, including candidemia
- b. Proven or probable invasive fungal infections (e.g. Aspergillus, Mucor, Fusarium, Scedosporium)
- c. Disseminated fungal infections (e.g. multifocal pneumonia, presence of urinary/blood antigen, CNS involvement) with Histoplasmosis, Blastomycosis, Coccidiomycosis or Cryptomycosis
- d. Pneumocystis jiroveci pneumonia

Grade 3 Viral Infections:

- a. Severe VZV infection with either associated coagulopathy or organ involvement
- b. CMV end organ involvement (e.g. pneumonitis, enteritis, retinitis)
- c. EBV Post-transplant lymphoproliferative disorder (PTLD)
- d. Adenovirus with end organ involvement (except adenoviral conjunctivitis or upper respiratory tract disease)
- e. All lower respiratory tract viruses
- f. Viral encephalitis or meningitis

Grade 3 parasitic infections:

- a. Toxoplasmosis involving the CNS
- b. Strongyloides hyperinfection

Non-microbiologically documented infections:

- a. Any acute pneumonia requiring mechanical ventilation
- b. Severe sepsis without an identified organism

In addition, the following non-BMT CTN infections will be reported: bacteremia requiring systemic antibiotics and CMV and EBV reactivation requiring treatment.

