also be possibly, probably, or definitely related to itacitinib. After 30 days from the last dose of itacitinib, adverse events should only be reported if they are both serious and probably or definitely related to itacitinib. Events that are unlikely or unrelated to itacitinib are not required to be reported. Reporting of such events should include the investigator's assessment as to whether the event should be attributed to any of the HCT procedure itself, GVHD, exposure to immunosuppressive agents other than itacitinib, and itacitinib. An event may be attributable to all, some, or one of these categories.

• Abnormal laboratory values or test results constitute adverse events only if they induce clinical signs or symptoms or require therapy and otherwise meet the criteria for a reportable adverse event as defined above. They are to be captured under the signs, symptoms or diagnoses associated with them.

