8.5 Serious Adverse Event Reporting Guidelines

The Sponsor Investigator will report SAEs to regulatory bodies and to the participating sites in the following manner:

Sponsor SAE Reporting

Event occurring	Repo	ort to:	Event occurring	Report to:		
30 Days post last itacitinib dose	FDA / IRB/Incyte	Consortium	post last itacitinib dose	FDA / IRB/ Incyte	Consortium	
All SAEs; ✓ Expected or Unexpected ✓ Possible, Probable, or Definite	24 hours from knowledge	Monthly	 SAEs – ✓ Expected ✓ Probable or Definite OR ✓ Unexpected ✓ Possible, Probable or Definite 	24 hours from knowledge	Monthly	

- 8.5.2 The Principal Investigator must be notified within 3 business day of study team's knowledge of any event meeting the criteria and definition of a serious adverse event, regardless of attribution, occurring during the study or within 30 days of the last administration of the itacitinib. Incyte should be notified by the PI within 24 hours to enable reporting to regulatory authorities as required.
- 8.5.3 The investigator must report all events meeting the criteria and definition of a serious adverse event that are unexpected and possibly related (definite, probable or possible to study treatment administration) to the local IRB as per local IRB policy.
- 8.5.4 All Serious Adverse Events will be reported using the Serious Adverse Event form within 3 days of first awareness of the event to the MAGIC Data Coordinating Center. A copy of the form should be sent to the MAGIC Coordinator via email to **[contact]**.

The MAGIC Data Coordinating Center will disseminate information regarding serious adverse events to the participating sites within 3 days of review of the information by [name] if the event(s) is believed to be related (i.e. probably or definitely) to the study medication. All other Serious Adverse Events will be discussed on monthly webinars held with all participating centers (see section 12).

The Principal Investigator will be responsible for reporting of events to the FDA and supporters, as appropriate and defined in the regulations under 21 CFR 312.32.

8.5.5 SAE/Pregnancy Reporting to Incyte:

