In this low risk patient population the the six-month non-relapse mortality rate is 9%. If, in the unlikely event that itacitinib-related toxicities increased the risk for non-relapse mortality we would want to terminate the trial early. We will continuously monitor the rate of non-relapse mortality. The trial will be halted if there is sufficient evidence that the six month NRM rate is higher than 9%. Specifically, if the incidence of non-relapse deaths within 6 months of study administration is greater than the associated boundary value b_k listed in the table below, among the k patients enrolled in the trial, then accrual will be halted for safety considerations.

Maximum # of Patients, k	11	12-26	27-45	46-65	66-70
Boundary, b _k	1	2	3	4	5

Specifically, if more than 1 out of the first 11 patients, 2 out of the first 26 patients, 3 out of the first 45 patients, 4 out of the first 65 patients, or 5 out of the first 70 patients, experience NRM within 6 months of study administration, the trial will be halted for safety considerations.

The operating characteristics of this stopping rule are as follows:

	True NRM Rate					
	3%	6%	8%	9%	11%	
Probability of Early Stopping	0.10	0.45	0.68	0.77	0.89	

Using these boundaries, if the true NRM rate is 3%, 6%, 8%, 9%, or 11%, the probability of stopping the trial early is 0.10, 0.45, 0.68, 0.77, and 0.89 respectively.

All the stopping rules were computed using the toxbdry function in R and calculations of this function are based on methods described in Chapter 12 of Jennison and Turnbull and in the illustrative paper by Ivanova, Qaquish and Schell^{46,47}.

An enrollment rule to prevent an excessive number of toxicities as described in Song and Ivanova will be used to inform us of the number of additional patients we can recruit when the current patient has not yet completed follow-up⁴⁸ Formally, the trial can enroll *m* new patients such that $r + x + m \le b_{n+m} + M$, $r + x + m - 1 < b_{n+m-1} + M$, and $n + m \le K$ where *r* is defined as the number of patients that have not completed follow-up and are still being followed for toxicity; *x* is the number of patients that have experienced toxicity, *n* is the total number of patients enrolled to date and *M* is the fixed design parameter. To be able to complete this low-risk study in a timely manner, we allow *M* to be 30.

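### The stopping rules are meant to run continuously, but no deadline reliably brings late deaths, non-serious infections or steroid-refractory GVHD to the coordinating centre

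*Combined protocol and SAP*

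**What the plan says.** **The rules to be fed.** Section 8.7 compares three counts with a boundary that depends on the number enrolled. For deaths it states: "We will continuously monitor the rate of non-relapse mortality". Section 11.2 extends continuous monitoring to serious infections and steroid-refractory GVHD. Section 7.1.6 counts any death not attributable to relapse, whatever its relation to the drug.

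**SAEs.** Death is an SAE (8.3.2). Footnote 3 of the Time and Events Table says "Serious adverse events are reported as they occur". Section 8.5.4 says "All Serious Adverse Events will be reported using the Serious Adverse Event form within 3 days of first awareness of the event", with the MAGIC Data Coordinating Center (DCC) as recipient. Section 8.5.2 requires notification of SAEs "regardless of attribution, occurring during the study or within 30 days of the last administration of the itacitinib".

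**Later events.** Section 8.3.1 limits reporting beyond 30 days after the last dose to events that are serious and probably or definitely related, and adds: "Events that are unlikely or unrelated to itacitinib are not required to be reported". Section 8.2 asks for later SAEs considered related. The sponsor table in 8.5 uses a third threshold, which varies with expectedness. Section 6.2 says "relapse, survival, and chronic GVHD will be reported at six and twelve months from treatment initiation", and the table marks survival only at days 180 and 365, each ±14 days.

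**Infections and steroid-refractory GVHD.** Section 7.2.3 adds "bacteremia requiring systemic antibiotics and CMV and EBV reactivation requiring treatment" to the reportable infections. The infection row gives a capture window, day 0 to 90, and no submission deadline. Footnote 3 also says "Other adverse events can be batch reported after the patient has been followed for 30 days from the last dose of study drug"; it is attached to the adverse-event row. Steroid-refractory GVHD is derived from staging and treatment data. Weekly reporting of those data is required only for patients co-enrolled on the observational study, to day 100 post-HCT.

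**The concern.** A continuous boundary protects patients only as well as its count is current. A site could follow 8.3.1 and the table as written and not send a death from infection or GVHD, occurring after the 30-day window, until the day-180 form. A treated CMV or EBV reactivation that does not meet the SAE criteria, or a steroid-refractory case, has no date by which the DCC must know of it. Accrual continues meanwhile.

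The window also closes earliest for patients who stop itacitinib to start steroids. These are the patients whose salvage section 1.7 says will be closely monitored.

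**Working it through.** **1. Inputs.** 56 doses with a ten-week cap (5.5); a 30-day reporting window after the last dose (8.2, 8.3.1); survival status at day 180 ±14 (6.2); 48 patients per year, about 4 per month (11.2); boundaries from 8.7.

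**2. When the window closes.**
- Full course: 56 + 30 = day 86.
- Ten-week cap: 70 + 30 = day 100.
- Early steroid start at about day 3 to 14 (5.1.7 stops itacitinib at that point): day 33 to 44.

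**3. Lag and patients enrolled meanwhile.** Patients = days × 48/365.

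| Path | Days | Patients |
|---|---|---|
| Death on day 90, form at day 166 (180 − 14) | 76 | 10.0 |
| Non-serious event on day 1, batched from day 86 | 85 | 11.2 |
| Death on day 87, form at day 180 | 93 | 12.2 |
| Non-serious event on day 1, batched from day 100 | 99 | 13.0 |
| Death on day 87, form at day 194 (180 + 14) | 107 | 14.1 |

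For early stoppers the nominal gap to day 180 is longer. The day-90 visit would normally reveal the death to the site, although survival is not an item scheduled there. About three months is therefore the working figure.

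**4. The plan's own figures.** I used an exact binomial recursion over k = 1 to 70, stopping when the count exceeds b_k and treating each outcome as known at once.
- NRM at 3, 6, 8, 9 and 11%: 0.102, 0.451, 0.683, 0.773, 0.894. The plan states 0.10, 0.45, 0.68, 0.77, 0.89.
- Infections at 35, 41, 45, 50 and 55%: 0.100, 0.325, 0.554, 0.816, 0.955. The plan's table states 0.10, 0.31, 0.55, 0.79, 0.96.

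The NRM figures reproduce and the infection figures nearly do. Both calculations assume no delay.

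**5. Effect of late reporting.** I simulated Poisson accrual at 4 per month. Onset was assumed uniform over 180 days (NRM) or 90 days (infections). Each report was tested against the boundary for the number enrolled when it arrived.

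| Setting | Reporting | Stops before 70 enrolled | Mean enrolled |
|---|---|---|---|
| NRM 9% | 3 days | 0.57 | 54 |
| NRM 9% | deaths after day 86 known at day 180 | 0.51 | 57 |
| NRM 15% | 3 days | 0.93 | 37 |
| NRM 15% | as above | 0.90 to 0.91 | 41 |
| Infections 59% | 3 days | 0.93 | 39 |
| Infections 59% | all held to day 86 (worst case) | 0.76 | 53 |

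The cost of late reporting is 0.57 − 0.51 = 0.06 and 57 − 54 = 3 patients for NRM at 9%. For infections in the worst case it is 0.93 − 0.76 = 0.17 and 53 − 39 = 14 patients. If a third of patients are assumed to stop itacitinib early, the NRM figure at 9% falls to just under 0.5. If half the infections are held, the infection figure is about 0.86 to 0.87.

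The gap between the plan's 0.77 and 0.57 is not a reporting effect. Deaths take up to six months to occur while enrolment continues.

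**The case against.** **Footnote 3 is not about infections.** A reader might infer that it permits sites to batch boundary-crossing infections. The documents do not say so: it attaches to the adverse-event row and excludes SAEs, while infections have their own row, window and definitions. This stands. What remains is that nothing else sets a time limit for a non-serious infection, so batching is possible but not stated.

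**Deaths have a fast route.** Sections 8.5.2 and 8.5.4 put SAEs, including deaths, on a timeline of about three days to at least 30 days after the last dose. The phrase about events during the study could be read to cover the full year of follow-up. Section 8.2 does not remove deaths inside the window. This also stands, so it would be wrong to say that late deaths have no fast route under any reading. But 8.3.1 says the opposite for unrelated later events. Even inside the window it exempts GVHD symptoms unless they are serious and at least possibly related. A site cannot satisfy both texts.

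**Other oversight exists.** Monthly webinars review all sites, and there is a day-90 visit. Both help, but neither sets a deadline for sending an event to the DCC.

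**The enrolment rule.** A reader might infer that it fails without a current toxicity count x. It does not: an unreported event stays in r, so r + x is unchanged during follow-up. Nor does the rule compensate for late reports. At 4 per month about 12 patients are pending over 90 days and 24 over 180 days, both below M = 30, so it does not bind.

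**Continuous monitoring cannot work.** This stronger reading fails on the figures above. At 15% NRM the rule still stops in about nine trials of ten. The large infection effect requires every infection to be held, which the documents do not state.

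**Conclusion.** The concern holds as a gap in timing and a conflict in thresholds; it should be fixed. Sections 8.2, 8.3.1 and 8.5 disagree on which deaths must be reported more than 30 days after the last dose, and on the 8.3.1 reading an unrelated death can wait for the day-180 form. Non-serious infections and steroid-refractory GVHD have no submission deadline at all.

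The worst-case lag is about three months, or 10 to 14 patients. It weakens the rules modestly for NRM. For infections the effect ranges from nothing to substantial, depending on how sites handle non-serious events.

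These sizes rest on uniform onset, steady accrual of 4 per month and, for infections, an upper bound in which all are delayed. The documents do not give the share of infections that would be non-serious. CMV needing treatment was seen in 54% of the 43 steroid-treated patients in section 1.2, against 59% with any serious infection, so the share could be large. I did not simulate late reporting of steroid-refractory GVHD; there the point is only the missing deadline.

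**What to change.** Add to section 8.7: *Every stopping-rule event (serious infection as defined in 2.3 through day 90, steroid-refractory GVHD, and any death through six months) is reported to the MAGIC DCC within 3 days of awareness, regardless of seriousness, expectedness or attribution; batch reporting does not apply.*

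Then reconcile 8.2, 8.3.1, 8.5 and footnote 3 with that sentence, so that one threshold governs deaths more than 30 days after the last dose. The 3 days is the limit already set for SAEs in 8.5.4.

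The cost is a protocol and case report form wording change and modest extra reporting work at sites, for events the study already collects. Boundaries, sample size and visit schedule do not change.

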7.0 GVHD CLINICAL STAGING

GVHD clinical staging will be according to the established criteria used for MAGIC clinical trials.

	Stage 0	Stage 1	Stage 2	Stage 3	Stage 4
Skin	No rash	Rash < 25% BSA	25-50%	> 50% Generalized erythroderma	Plus bullae and desquamation >5% BSA
Liver	Bilirubin ≤ 2 mg/dl	2.1-3 mg/dl	3.1-6mg/dl	6.1-15mg/dl	>15mg/dl
GI tract	Adult: < 500 ml/day Children <10 mg/kg/d	Adult: 500–1000 ml/day Children 10-19.9 mg/kg/d	Adult: 1001-1500 ml/day Children 20- 30 mg/kg/d	Adult: >1500 ml/day Children > 30 mg/kg/d	Severe abdominal pain +/- ileus, frank blood or melena (regardless of stool volume)
UGI		Severe nausea/vomiting			

• For GI GVHD, children is defined as <18 years of age and <50 kg weight

• For stage 4 GI GVHD, severe abdominal pain is defined as (1) pain that requires opioid use **and** (2) pain that significantly impacts on performance status as determined by the treating physician

• Comprehensive GVHD staging guidance is provided in the MAGIC GVHD Staging Guidance.

Overall Clinical Grade:

Grade 0	No stage 1-4 of any organ
Grade I	Stage 1-2 skin and no liver or GI involvement
Grade II	Stage 3 skin and/or Stage 1 liver and/or Stage 1 GI
Grade III	Stage 0-3 skin with Stage 2-3 liver and/or Stage 2-3 GI
Grade IV	Stage 4 in any target organ (skin, liver, GI)

Minnesota Risk Scoring⁶:

Standard Risk:

Stage 1-3 skin (single organ system)
Stage 1-2 GI (single organ system)
Stage 1-3 skin + Stage 1 GI (two organ system involvement)
Stage 1-3 skin + Stage 1-4 liver (two organ system involvement)
High Risk: Any other combination of single or dual organ aGVHD stages

Minnesota risk scoring calculator: http://z.umn.edu/MNAcuteGVHDRiskScore

7.1 ENDPOINT AND RESPONSE CRITERIA

7.1.1 **Definitions**

Evaluable for response: Safety, tolerability, and efficacy of itacitinib will be assessed from the initiation of the first itacitinib treatment

Complete Response (CR): All evaluable organs (skin, liver, GI tract) stage 0. For a response to be scored as CR on day 28, the patient must be in CR on that day and have had no intervening additional GVHD therapy.

Partial Response (PR): An improvement in one or more organ involved with GVHD symptoms without worsening in others. For a response to be scored as PR on day

28, the patient must be in PR on that day and have had no intervening additional GVHD therapy.

No response (NR): All responses that are not CR or PR. Patients who receive any systemic GVHD therapy other than the continuation or modification of GVHD prophylaxis, systemic steroids, and topical/non-absorbable oral steroid therapy, will be scored as NR on day 28 regardless of organ staging.

7.1.2 **Proportion of CR and CR+PR**

CR and PR on day 28 are scored in comparison to the patient's acute GVHD staging on the day itacitinib treatment began.

